9.8.2 Quality review

Quality review will follow a sequential, risk-based approach: in a first step the site's training status will be assessed via standardized telephone interviews. In a second step, source data verification will be conducted. The purpose is to review the documented data for completeness and plausibility, adherence to the OS protocol and verification with source documents.

Detailed measures for quality reviews will be described in the Quality Review Plan (QRP). The QRP is available upon request (see Annex 1).

9.8.3 Storage of records and archiving

Bayer will ensure that all relevant documents of this study will be stored after the end or discontinuation of the study for at least 25 years. Any data as well as programs from statistical programming performed to generate results will be stored within the programming system for at least 25 years.

Participating study sites are required to archive and retain study documents for the period stipulated by local regulations, considering possible audits and inspections from Bayer AG and/or local authorities.

9.9 Limitations of the research methods

Because of the non-interventional study design and limitations inherent to observational studies, findings generated from this study are subject to biases, such as selection bias, limitations to availability of historical medical data, and differences in treatment or reporting owing to local guidelines.

Although the study aims to include patients from a variety of geographic regions, there may be local limitations that reduce the representativeness of patients recruited, such as patient access to recruiting physicians (including differences in patient profile in specialized, recruiting sites vs local general practice), finerenone availability and reimbursement, and decisions relating to local standard of care.

9.10 Other aspects

NA

10. Protection of human subjects

10.1 Ethical conduct of the study

This study is an observational study where finerenone is prescribed in the customary manner in accordance with the terms of the marketing authorization. There is no assignment of a patient to a particular therapeutic strategy. The treatment decision falls within current practice and the prescription of the medicines is clearly separated from the decision to include the patient in the study. No additional diagnostic or monitoring process is required for participation or during the study. Epidemiological methods will be used for the analysis of the collected data.

10.2 Regulatory authority approvals/authorizations

The study will be carried out within an approved indication in accordance with guidelines and regulations of EMA, FDA and applicable local laws and regulations (e.g. Regulation (EU) No 520/2012 [12]). Recommendations given by other organizations will be followed as well (e.g. EFPIA [13], ENCePP [14]).

In addition, the guidelines on good pharmacovigilance practices (GVP module VI [15]).

10.3 Independent ethics committee (IEC) or institutional review board (IRB)

In all countries where reference to an IEC/IRB is required, documented approval from appropriate IECs/IRBs will be obtained for all participating centers prior to study start. When necessary, an extension, amendment or renewal of the IEC/IRB approval must be obtained and also forwarded to the study initiator and funder. The IEC/IRB must supply to the study initiator and funder, upon request, a list of the IEC/IRB members involved in the vote and a statement to confirm that the IEC/IRB is organized and operates according to applicable laws and regulations.

10.4 Patient information and consent

Before documentation of any data, informed consent is obtained by the patient.

Informed consent forms will be provided for persons who are capable to give their consent. For adult patients not capable to give their consent, the legal representative should give the consent.

21785 FINE-REAL; V 1.0; 09 February 2022; based on template version 15

Page 30 of 48

If a patient or the legally acceptable representative is unable to read, an impartial witness (independent of Bayer and the investigator) will be present during the entire informed consent discussion. The informed consent form and any other information to be provided to patients, is read and explained to the patient or the patient's legally acceptable representative. The patient or the patient's legally acceptable representative have to orally consent to the patient's participation in the study and, if capable of doing so, have to personally sign and date the informed consent form. Thereafter the witness will personally sign and date the consent form.

In countries where required by law or regulation, the investigator must have the IECs/IRB written approval/favorable opinion of the informed consent form and any other information to be provided to patients prior to the beginning of the observation.

10.5 Patient insurance

In this observational study, data on routine treatment of patients in daily practice are documented and analyzed with the help of epidemiological methods. Treatment including diagnosis and monitoring of therapy follows exclusively routine daily practice. Current medical daily practice is observed, and for the patient no risks beyond regular therapy exist – there is no additional hazard arising from study participation. As no study related risks exist, there is no need to protect the patient additionally by a patient insurance. The general regulations of medical law and the professional indemnity insurance of the investigators and, respectively, the institutions involved provide sufficient protection for both patient and investigator.

No study medication will be provided to patients. Thus, product insurance is covered by the existing product liability.

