9.1 Study design

This international study is a prospective, non-interventional multicenter, single arm study of patients with a diagnosis of CKD associated with T2D who are newly prescribed finerenone under routine

21785 FINE-REAL; V 1.0; 09 February 2022; based on template version 15

Page 16 of 48

treatment conditions. It is planned to enroll 4000 patients with a diagnosis of CKD and T2D for whom the decision was taken by the treating physician to initiate treatment with finerenone. Patients will be recruited within a period of approximately 30 months and followed up until 30 days after permanent discontinuation of finerenone, or until death, withdrawal of consent, end of study, or loss-to-follow-up, whichever occurs first. In case of a temporary finerenone treatment pause of ≤ 6 months, patients should stay in the study and followed up as planned. Finerenone treatment pauses of > 6 months are considered as permanent treatment discontinuation and end of observation should be documented in such cases (please also refer to section 9.2.5). End of study will occur 12 months after last patient first visit, allowing that each patient can be followed up for a minimum of 12 months.

In the event that the Chinese Heath Authority requires this study to be a PAC, then free drugs-finerenone will be provided for Chinese patients as requested per local guidelines for such studies. All study drugs are from commercial supplies and relabeled according to the relevant requirements. All study drugs will be distributed by an authorized drug responsible person such as pharmacist or study nurse.

9.1.1 **Primary endpoint(s)**

The primary endpoint is to describe treatment pattern in patients with CKD and T2D treated with finerenone, based on:

- Clinical characteristics of patients with CKD and T2D
- Reasons for introducing finerenone
- Reasons for discontinuation of finerenone
- Planned and actual duration of treatment with finerenone
- Dosing of finerenone
- Use of secondary therapies (concomitant medication) in patients with CKD and T2D.

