9.7 Data analysis

9.7.1 Statistical considerations

Statistical analyses will be of explorative and descriptive nature. The study is not intended to test pre-defined statistical hypotheses.

All variables will be analyzed descriptively with appropriate statistical methods: categorical variables by frequency tables (absolute and relative frequencies) and continuous variables by summary statistics (i.e. mean, standard deviation, minimum, median, quartiles and maximum).

All analyses will be performed for the total study population (overall population) and separately for each participating country if patient numbers are sufficient and if required for local reasons. Whenever reasonable, data will be stratified by subgroups (e.g. age, sex, baseline characteristics).

All therapies documented in the following forms will be coded using the latest version of the World Health Organization Drug Global available at time of database lock.

• Prior and concomitant medication

Any diagnoses/diseases/event terms documented in the following forms will be coded using the latest Medical Dictionary for Regulatory Activities (MedDRA) version:

- Co-morbidities (medical history, concomitant diseases)
- Adverse events

Interim analysis will consist of demographic and baseline data of patients enrolled as well as available safety data. Further details will be given in the statistical analysis plan (SAP).

All statistical details including calculated variables and proposed format and content of tables will be detailed in the Statistical Analysis Plan (SAP). The SAP will be finalized before study database lock. The SAP is available upon request (see Annex 1).

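### Section 10.5 rules out any supplied study drug, but section 9.1 foresees free finerenone in China if a commitment study is required, and no treatment-pattern result without those patients is fixed

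*Protocol*

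**What the plan says.** **Supply.** Section 10.5 (Patient insurance) states "No study medication will be provided to patients", with no exception. Its next sentence depends on this: "Thus, product insurance is covered by the existing product liability".

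Section 9.1 (Study design) sets out a conditional exception: "In the event that the Chinese Heath Authority requires this study to be a PAC, then free drugs-finerenone will be provided for Chinese patients". It adds "All study drugs are from commercial supplies and relabeled according to the relevant requirements" and "All study drugs will be distributed by an authorized drug responsible person such as pharmacist or study nurse". Section 7 (Rationale and background) says approval in mainland China may come with a request for a post-authorization commitment study, and gives meeting that request as the reason China was added.

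**Status.** Section 10.1 (Ethical conduct) describes a study in which "finerenone is prescribed in the customary manner in accordance with the terms of the marketing authorization", with prescribing kept separate from the decision to include the patient. It makes no exception for China.

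**Analysis.** Section 8.1 sets the primary objective as treatment patterns in routine clinical practice. Section 9.1.1 includes treatment duration and the reasons for starting and stopping finerenone. Section 9.7.1 begins its population rule with "All analyses will be performed for the total study population (overall population"; the same sentence allows results by country where numbers suffice and local reasons require them. Section 9.5 plans 4,000 patients, with a subset of 400 from China that has its own precision table. Section 9.9 names availability and reimbursement as local limitations but does not mention study-supplied drug.

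**The concern.** Two sections of one protocol disagree on whether the study hands out drug, and the insurance reasoning rests on the section without the exception. An ethics committee or authority reading 10.5 alone would be told something that 9.1 may make false.

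The second issue is interpretation. Drug that is free, relabelled and handed out through the study is not obtained in the way routine patients obtain it. Cost and access are plausible reasons for staying on a drug or stopping it, and both duration and reasons for stopping are part of the primary endpoint. If supply applies, up to a tenth of the planned sample would enter a description labelled routine practice under different access conditions. Nothing in the protocol identifies these patients or fixes a result without them.

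**Working it through.** **1. The supply statements side by side**

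| Point | Section 9.1 | Section 10.5 |
|---|---|---|
| Drug supplied by the study? | Yes in China, if a commitment study is required | No, without exception |
| Form | Commercial stock, relabelled, handed out by an authorized person | Not applicable |
| Insurance | Not addressed | Existing product liability, inferred from no supply |

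If the condition is not met, the sections agree in practice. If it is met, the 10.5 sentence is false for Chinese patients and its insurance conclusion loses its stated premise. Section 7 shows that the condition was foreseen when the protocol was written.

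**2. The plan's own figures**

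The width of a 95% interval is 2 × 1.96 × √(p(1 − p)/n). At p = 50%:

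- n = 4,000: 2 × 1.96 × √(0.25/4,000) = 3.10 points; section 9.5 states 3.1%.
- n = 400: 2 × 1.96 × √(0.25/400) = 9.80 points; section 9.5 states 9.8%.

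Both reproduce. China's planned share is 400/4,000 = 10%.

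**3. What pooling can do to a percentage**

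Let C be the percentage in China and R the percentage elsewhere. The pooled value is 0.9R + 0.1C, so it differs from the result without China by 0.1 × (C − R). The protocol gives no value for C − R, so the range below is assumed:

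| Assumed difference, China versus rest | Pooled shift |
|---|---|
| 5 points | 0.5 points |
| 10 points | 1.0 point |
| 20 points | 2.0 points |
| 30 points | 3.0 points |

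For scale only, the half-width 1.96 × √(p(1 − p)/4,000) is 0.9 points at 10%, 1.4 at 30% and 1.5 at 50%. The difference would have to be about 9, 14 or 15 points for the shift to equal it. Section 9.5 says that confidence intervals do not apply to treatment patterns, so this is a yardstick and not a planned criterion.

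**4. Limits of this arithmetic**

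- The one-tenth weight holds for percentages of all patients, and for means, at planned enrolment. For reasons among patients who stop, China's weight is its share of those who stop, which is unknown. Medians do not combine in this way.
- C − R mixes free supply with every other difference between countries. The effect of supply alone would be 0.1 × (China under free supply − China under routine supply), and the second term would not be observed if all Chinese patients were supplied.

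**5. Can the patients be identified?**

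The exposure variables in section 9.3.1 cover reasons, duration, dose and frequency, but not the source of the drug. The CRF is a stand-alone document that is not shown and may contain it. Country is a full substitute only if every Chinese patient is supplied throughout; it fails if the requirement arrives during enrolment.

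**The case against.** - **Supply is conditional.** A reader might infer that free drug is a settled part of the design. Section 9.1 ties it to a requirement by the authority, and section 7 calls the request potential. This stands; it limits the point to the case where the condition is met, but does not remove the contradiction.
- **Pooling is not the only view.** Section 9.7.1 allows country results and section 9.5 sizes the China subset. An authority request is a plausible local reason for a separate China presentation. This also stands. However, the country results are themselves conditional, and no section fixes a result without supplied patients. The layout of such a table could be left to the SAP, but the source of the drug has to be collected.
- **Prescribing precedes inclusion.** A reader might infer that free supply overturns the observational status claimed in 10.1. Sections 9.2.1 and 10.1 place the physician's decision before enrolment, under the local label, and the drug is commercial stock. The documents do not show that supply would drive the decision to start. What remains is that 10.1, like 10.5, takes no account of the exception.
- **Insurance.** A reader might infer that supplied patients would be uninsured. The documents do not settle whether existing product liability covers relabelled commercial drug. They show only that the reason given in 10.5 would no longer hold.

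**Conclusion.** The contradiction between 9.1 and 10.5 is certain on the text and takes effect if the commitment-study condition is met. It would then concern up to 400 of 4,000 planned patients.

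The effect on results is possible but unmeasured. On percentages of all patients, the pooled shift is one tenth of the China-versus-rest difference, so it is modest unless that difference is large. The China result is the more exposed, because there the effect of supply is not diluted; however precise, it would describe use under free supply and not routine access.

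A reader might go further and conclude that persistence and reasons for stopping are distorted, or put a number of points on the error in the China figure. The documents support neither. They give no discontinuation rate for either setting. Any such number would restate an assumed gap and would also assume that routine use in China matches routine use elsewhere, whereas section 9.9 expects local differences.

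The conclusion rests on enrolment as planned and on supply reaching all Chinese patients. It is worth correcting because the correction is cheap and protects the claim to describe routine practice.

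**What to change.** 1. Reconcile sections 9.1, 10.1 and 10.5 so that the no-supply and insurance text carries the same China condition as 9.1, and state the insurance basis for supplied drug.
2. Record for each patient whether finerenone came through routine supply or from the study.
3. If supply applies, keep the total population as planned, show the primary treatment-pattern tables with and without study-supplied patients, and present those patients separately. Restricting the primary population to routine supply is not needed; it could remove from the main result a cohort that was added to meet a regulatory request.
4. Name free supply as a limitation in section 9.9.

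The cost is wording, one CRF item and an extra set of tables. The tables without supplied patients would rest on about 4,000 − 400 = 3,600 patients. On the yardstick of section 9.5, the maximum width would be 2 × 1.96 × √(0.25/3,600) = 3.3 points instead of 3.1.

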10.6 Confidentiality

Bayer as well as all investigators ensure adherence to applicable data privacy protection regulation. Data are transferred in encoded form only. The entire documentation made available to Bayer does not contain any data which, on its own account or in conjunction with other freely available data, can be used to re-identify natural persons. The investigators are obligated to ensure that no documents contain such data.

All records identifying the subject will be kept confidential and will not be made publicly available. Patient names will not be supplied to Bayer AG. If the patient name appears on any document, it must be obliterated before a copy of the document is supplied to Bayer AG. Study findings stored on a computer will be stored in accordance with local data protection laws.

The investigator will maintain a list to enable patients' records to be identified in case of queries. In case of a report of a serious adverse event (SAE), the responsible pharmacovigilance person may ask for additional clarification. In that case, the company is not allowed to directly contact the patient. All additional information will be provided by the investigator.

11. Management and reporting of adverse events/adverse reactions

11.1 **Definitions**

Adverse event (AE): Any untoward medical occurrence in a patient administered a pharmaceutical product and which does not necessarily have to have a causal relationship (association) with this

21785 FINE-REAL; V 1.0; 09 February 2022; based on template version 15

Page 31 of 48

treatment. An AE can therefore be any unfavorable and unintended sign (including an abnormal laboratory finding), symptom, or disease temporally associated with the use of the product, whether or not related to the product.

Adverse Reaction (AR): an adverse reaction is a noxious and unintended response to a medicinal product. This includes adverse reactions which arise from:

- use of a medicinal product within the terms of the marketing authorization
- use outside the terms of the marketing authorization, including off-label use, overdose, misuse
- abuse and medication errors
- occupational exposure

An adverse reaction, in contrast to an adverse event, is characterized by the fact that a causal relationship between a medicinal product and an occurrence is suspected.

Serious adverse event/serious adverse reaction: an adverse event (AE) or adverse reaction (AR) is serious if it:

- results in death,
- is life-threatening
- requires inpatient hospitalization or prolongation of existing hospitalization.

A hospitalization or prolongation of hospitalization will not be regarded as a serious adverse event (SAE) if at least one of the following exceptions is met:

- o the admission results in a hospital stay of less than 12 hours;
- o the admission is pre-planned (i.e. elective or scheduled surgery arranged prior to the start of the study);
- o the admission is not associated with an AE (e.g. social hospitalization for purpose of respite care).

However, it should be noted that invasive treatment during any hospitalization may fulfill the criterion of 'medically important' and as such may be reportable as an SAE dependent on the clinical judgment. In addition, where local regulatory authorities specifically require a more stringent definition, the local regulation takes precedence;

- results in persistent or significant disability or incapacity
- is a congenital anomaly, birth defect or fetal mental impairment
- is medically significant:
 - Medical and scientific judgment should be exercised in deciding whether an AE/AR may be considered serious (due to an important medical event) because it jeopardizes the health of the patient or may require intervention to prevent another serious condition (death, a life-threatening condition, hospitalization or persistent or significant disability).

- o Examples of such events are:
 - invasive treatment during any hospitalization, in an emergency room or at home for allergic bronchospasm
 - blood dyscrasia or convulsions that do not require hospitalization
 - development of any drug dependency or abuse
 - lack of drug effect if the finerenone was used for the treatment of acute lifethreatening diseases (apply medical judgment) or reports of any transmission of an infectious agent via a finerenone

11.2 Collection

Starting with the first application of finerenone after enrollment into the study, all non-serious adverse events (AE) must be documented on the AE Report Form or in the CRF/EDC system and forwarded to the MAH within 7 calendar days (for OS inside the EU) or if required by local regulations of participating country)/ 30 days (for OS that involve only countries outside the EU) of awareness. All serious AEs (SAE) must be documented and forwarded immediately (within one business day of awareness). For each AE, the investigator or a delegate must assess and document the seriousness, duration, relationship to product, action taken and outcome of the event.

If a pregnancy in female participants occurs during the study, although it is not a serious adverse event itself, it should be documented and forwarded to the MAH within the same time limits as a serious adverse event. The result of a pregnancy will be followed-up according to applicable Bayer SOPs. Any data on abnormal findings concerning either the mother or the baby will be collected as adverse events.

The documentation of any AE/SAE ends with the completion of the observation period of the patient. However, any AE/SAE - regardless of the relationship and the seriousness - occurring up to 30 days after the last dose of finerenone within the study period has to be documented and forwarded to the MAH within the given timelines, even if this period goes beyond the end of observation.

As long as the patient has not received any finerenone within the frame of the study AEs /SAEs do not need to be documented as such in this observational study. However, they are part of the patient's medical history.

For any serious product-related AE occurring after study end, the standard procedures that are in place for spontaneous reporting have to be followed.

